 6.3 Day 180 Follow up 18

 6.4 Outcome measurements 18

 6.5 Collection and processing of biological samples 18

7. SERIOUS ADVERSE EVENTS 20

8. TRAINING	21
9. TIMELINE	21
10. DATA ANALYSIS	21
10.1 Primary Objectives	22
10.2 Secondary Objectives	23
10.3 Sample size	25
11. RISK MITIGATION	27
12 STUDY MANAGEMENT AND OVERSIGHT	29
12.1 Coordination	29
12.2 Local Governance	29
12.3 Ethical Review	30
12.4 Trial Advisory Group and Technical Steering Committee.....	30
12.5 Data Safety and Monitoring Board.....	30
12.6 Quality assurance.....	30
12.7 Data management	31
12.8 References	32
13 SITE IMPLEMENTATION PLANS	33
13.1 Bangladesh.....	33
13.2 India	37
13.3 Kenya.....	40
13.4 Malawi	44
13.5 Mali.....	47
13.6 Pakistan.....	50
13.7 Tanzania.....	53

STUDY OVERVIEW

Although the current WHO recommended management package for acute diarrhoea (ORS, zinc and feeding advice) has contributed to significant reductions in diarrhoea associated mortality, over half a million children continue to die annually as a result of acute diarrhoeal episodes. In addition, there is increasing interest in the rates of mortality in young children in the 90-180 days following an episode of acute diarrhoea. The long-term benefits of antibiotic administration may result from direct antimicrobial effects on pathogens or from other incompletely understood mechanisms including improved nutrition, alterations in immune tolerance or improved enteric function. Optimizing antibiotic treatment of acute diarrhoea episodes in very young children with severe disease may offer the opportunity to significantly reduce diarrhoea associated deaths in the 90-180 days following presentation for acute diarrhoea and may also improve growth. We propose to evaluate the efficacy of an antibiotic (azithromycin) delivered in a specific, targeted fashion to young children (< 2 years of age) at high risk of diarrhoea associated mortality in a multi-site randomized, double-blind, placebo-controlled trial. The study will evaluate the ability of the intervention to reduce mortality within 180 days of the acute diarrhoeal episode and improve nutritional status over the same period.

PROTOCOL VERSIONS AND AMENDMENT HISTORY

Vers ion	Date issued	Authors	Details of changes made	WHO ERC submission & status; dates and number
1.0	05.02.2016	Simon, [name]	Original document, submitted to the WHO ERC	Submitted 10.02.-16, conditionally approved 10.03.-16 (ERC.0002722)
2.0			Internal working document, not submitted to IRB	
3.0	01.05.2016	Simon, [name]	Provided clarifications based on comments by the WHO. No changes to study design	Submitted 09.05.-16, approved 14.07.-16 (pending site-specific protocols)
4.0			Internal working document, not submitted to IRB	
5.0			Internal working document, not submitted to IRB	
6.0	08.02.2017	[name], Simon, [name]	
Removed ciprofloxacin from study interventions; because of concerns about the safety of this antibiotic and a recommendation by a WHO expert group. Accordingly, removed “allergy to ciprofloxacin” from exclusion criteria, changed sample size, and edited analysis strategy to match the new 2-arm (vs. earlier 3-arm) design
 
Tightened inclusion criteria so that children with moderate stunting will not be enrolled, because of concerns about spread of antimicrobial resistance and recommendation by the WHO expert group: Relatedly, clarified objectives and methods for biological specimen collection and processing for analysis of bacterial resistance to antimicrobial agents.
 
Added number and cause of hospitalizations in outcome measures, based on requests from some local IRBs
 
Corrected some small errors in the previous version: Edited mid upper arm circumference (MUAC) cut-off to determine severe wasting in exclusion criteria, to match WHO and national criteria (from MUAC <110 mm to MUAC <115 mm); removed “visible wasting” from exclusion criteria (not operational); Added “participation in another interventional trial” as an exclusion criterion; Clarified the definition of some eligibility criteria
 
Made some technical edits to the document: Clarified the role and meeting modes of Trial Advisory Group, Trial Steering Committee, and Data Safety and Monitoring Board; Added a cover page with list of investigators, a table of contents and a table explaining the version history and edits to the protocol; Edited informed consent document to reflect the changes in the study design; Added an informed consent document to be used for a guardian interview on the cause of death if a study participant dies
	Submitted 08.02.-17, clarification sought 24.02.2017
7.0	01.03.2017	[name], Simon, [name]	Clarified the storage and analysis of biological specimens, edited informed consent on the same.	Submitted 01.03.-17 Approved 07.03.2017
8.0	30.10.	[name],	Added a possibility to collect stool samples by rectal	To be submitted to the

Vers ion	Date issued	Authors	Details of changes made	WHO ERC submission & status; dates and number
	2017	Simon, [name]	swabs. Added a mother as a possible household contact from whom a nasopharyngeal swab can be collected for antimicrobial resistance analysis. Added a follow-up visit to day 180 for all participants. Corrected a typo in participant numbers in Figure 1. Edited informed consent on changes	Submitted 02.03.-18 Approved 25.03.2018
9.0	21.12.2018	Simon	Modified Secondary Outcomes Modified Analysis Plan based on the secondary outcomes changes Removed [name] as WHO Coordinator Adjusted sample size for AMR component	Submitted to the WHO ERC after site approvals of the modification

0. BACKGROUND

The problem

Despite dramatic reductions in childhood mortality during the past three decades, an estimated 6.3 million children died in 2013 before reaching their 5th birthday. The reduction in mortality has been especially impressive for diarrhoeal disease. In 1980, an estimated 4.6 million under-five children were dying every year because of diarrhoea (2) while in 2013, the number of deaths due to diarrhoea in this age group was reduced to 0.6 million per year (3). This very significant reduction was partly due to the diarrhoea control strategy implemented throughout the world since the 1980s which includes the treatment/prevention of dehydration with ORS and/or IV fluids, administration of zinc, and feeding advice.

There continue to be over 600,000 deaths/year in under-five children attributed directly to diarrhoea. Data from the Global Enterics Multicenter Study (GEMS), a large multi-center observational study, suggest that only 1/3 of diarrhoea associated deaths occur in the first week following diagnosis. When follow-up visits were conducted 50-90 days after the enrolment encounter, the timing of deaths among children with diarrhoea was as follows: 34% occurred on days 0–7 after enrolment, 33% on days 8–21 and 33% after day 21 (4). In addition, diarrhoea episodes considered as moderate to severe cases had an 8.5fold higher risk of death during the 50-90 day follow-up period compared to their matched controls in spite of appropriate treatment of the episode, including ORS, zinc and feeding advice (4). The risk of death was significantly associated with the degree of stunting at enrolment. Although 26% of deaths in cases occurred during the enrolment encounter at the health care facility and 19% during a subsequent medical contact, importantly, 55% occurred at home or outside of a medical facility. Most deaths in patients with diarrhoea occurred in infants (56%) and toddlers (32%). These data suggest that current estimates which predominantly capture immediate deaths and those that occur in a health facility may dramatically underestimate diarrhoea associated mortality.

These data also suggest that a proportion of deaths due to diarrhoea, especially in young children and in children with moderate to severe diarrhoea, may not be avoided just by using

the current treatment recommendations for ORS, zinc and continued feeding. This is confirmed by a recently conducted verbal autopsy study which showed that most children (70%) who died from diarrhoea had received ORS or intravenous solutions (5) prior to death. Additional treatment may be necessary in these children to reduce diarrhoea mortality.

Potential Solution:

The World Health Organization currently recommends the use of antibiotics only for the treatment of dysentery (as a proxy for suspected shigellosis and cholera) (6, 7). However, recent data suggest (4) that multiple bacterial and parasitic pathogens are important in the aetiology of moderate to severe diarrhoea and some of these pathogens are significantly associated with death in the 90 days following a diarrhoea episode (Cryptosporidium, typical enteropathogenic *E. coli* (tEPEC) and ST-EPEC).

Given the demonstrated risk of death associated with diarrhoea in specific subsets of children with malnutrition and those with severe illness at baseline, expanding the use of antibiotics for a subset of children with diarrhoea associated with high risk of subsequent mortality (high risk diarrhoea) may be an important intervention to reduce diarrhoea associated mortality.

Recently published data from the GEMS study suggest that least one putative pathogen can be identified in over 80% of children presenting with moderate-severe diarrhoea. In addition to viruses (including rotavirus), bacterial pathogens, including *Shigella* and pathogenic *E. coli* species were commonly identified across all seven of the sites, all with moderate-to-high under-5 mortality in sub-Saharan Africa and South Asia (4). Other authors have also demonstrated that visible blood in stool is a poor indicator of *Shigella* infection in children with diarrhoea (Pavlinac, ASTMH 2014). Taken together, these data suggest that current treatment guidelines may be missing the opportunity to appropriately provide antibiotics to a group of young children at particularly high risk of diarrhoea associated mortality.

Data suggest that 80-90% of all children with diarrhoea currently receive antibiotics, despite WHO guidelines restricting antibiotics to a small subset with dysentery or cholera. The use of targeted empiric antibiotics for a small subgroup of severely ill children at high risk of death may also potentially lower antimicrobial resistance if such children defer to the use of more appropriate antibiotics than are commonly used in practice now (despite WHO guidelines) and if other children are less likely to use antibiotics based on an assessment of their being at lower risk. In addition, data from trials of antibiotics in acute respiratory illness also suggest that when clear guidelines are provided for the use of antibiotics in high risk children, antibiotic use decreases and resistance among isolated pathogens is reduced (10, 11).

After discussions with antimicrobial resistance experts at WHO and externally, we feel that careful documentation of the association between clinical failure and the development of resistance in the community during this trial would be useful to allow careful risk/benefit assessment of any proposed policy change if a mortality reduction benefit is shown. In a complementary linked study, we propose to study antimicrobial resistance to multiple antibiotics, among *Escherichia coli* and *Streptococcus pneumoniae* isolates in stool samples collected from a subgroup of participants at enrolment and in stool samples and naso-

pharyngeal swabs collected from the same subgroup of participants and their close household contacts at the 90-day and 180 days follow-ups. Additionally, we propose that stool be collected and stored at -80°C from all participants at enrolment for molecular detection of pathogens and identification of antimicrobial resistance genes at a later date. For the same purpose, we also propose to store stool and nasopharyngeal swab samples from the subgroup of participants at the 90-day and 180-day follow-ups.

Safety profile of azithromycin: A review of studies having used azithromycin in young children concluded that "...azithromycin given as a suspension once daily for 3 days is well tolerated and can be used safely for the treatment of acute bacterial infections in children of all ages. Even in very young children, there are no concerns regarding safety or tolerance." (13).

References

1. OBJECTIVES

1.1 Primary Objectives:

1. To compare rates of all-cause mortality in the 180 days following enrolment for an episode of high risk diarrhoea without dysentery among children 2 to 23 months of age living in low resource settings who are randomized to receive a 3-day course of azithromycin or placebo.
2. To compare the change in linear growth (Δ LAZ) in the 90 days following enrolment for an episode of high risk diarrhoea without dysentery among children 2 to 23 months of age living in low resource settings who are randomized to receive a 3-day course of azithromycin or placebo.

1.2 Secondary Objectives:

1. To compare changes in markers of acute malnutrition (Δ MUAC and Δ WLZ and Δ weight) in the 90 days following an episode of high risk diarrhoea without dysentery among children 2 to 23 months of age living in low resource settings who are randomized to receive a 3-day course of azithromycin or placebo.
2. To evaluate (as determined by verbal and social autopsy- VASA) cause-specific mortality rates across randomization arms in the 180 days following an episode of high risk diarrhoea without dysentery among children 2 to 23 months of age living in low resource settings who are randomized to receive a 3-day course of azithromycin or placebo.
3. To compare the proportion of children hospitalized in the 90 days following enrolment for an episode of high risk diarrhoea without dysentery among children 2 to 23 months of age living in low resource settings who are randomized to receive a 3-day course of azithromycin or placebo.
4. To compare the proportion of children hospitalized or died in the 90 days following enrolment for an episode of high risk diarrhoea without dysentery among children 2 to 23 months of age living in low resource settings who are randomized to receive a 3-day course of azithromycin or placebo.
5. To compare the proportion of children hospitalized or died in the 10 days following enrolment for an episode of high risk diarrhoea without dysentery among children 2 to 23 months of age living in low resource settings who are randomized to receive a 3-day course of azithromycin or placebo.
6. To compare the proportion of strains of *Escherichia coli* (*E. coli*), isolated from stools, resistant to selected antibiotics at enrolment among the study population. Since children entering later into the trial are coming from the same communities, they can serve as a comparator group indicative of the community level of resistance.
7. To compare the proportion of strains of *E. coli*, isolated from stools, and *Streptococcus pneumoniae* (*S. pneumoniae*), isolated from nasopharyngeal swabs, resistant to selected antibiotics at DAY 90 and DAY 180 in a randomly selected sub-sample of children enrolled in the study and their siblings or close household contacts (children under five years of age living in the same household under the care of the same primary caregiver).

2. SIGNIFICANCE AND IMPLICATIONS

Among specifically targeted children at high-risk of diarrhoea-associated mortality we propose to determine the efficacy of an antibiotic (azithromycin), compared to placebo, in reducing risk of death and linear growth faltering in the six months following an episode of severe diarrhoea. Secondly, we will evaluate the risk of individual and community-level antibiotic resistance in bacterial enteric and nasopharyngeal infections. These aims will inform future diarrhoea case

management guidelines by empirically determining the potential benefits and harms associated with targeted antibiotic use in children with severe diarrhoea.

[figure not shown]
2.1 Study sites

The study will be conducted in health facilities in 7 countries in South Asia (Bangladesh, India and Pakistan) and Sub-Saharan Africa (Kenya, Malawi, Mali and Tanzania). The countries have been selected based on study site characteristics as well as the strengths and experience of the country team in conducting large intervention trials. Within each country, 2-10 individual health facilities will be the sites of patient enrolment.

2.2 Study Design

We propose a randomized, multi-country, multi-site, double-blind, placebo-controlled clinical trial. A total of 11,500 children (5,750 per treatment arm) will be enrolled in the study across the 7 countries and followed up for 180 days (Figure 1).

Figure 1. Trial design

2.3 Eligibility criteria

2.3.1 Inclusion criteria (all of):

- Children aged 2 – 23 months, presenting to a designated health care facility at a participating study site **WITH**
- Diarrhoea per caregiver perception **AND** at least 3 loose or watery stools in the previous 24 hours,
- Diarrhoea for less than 14 days prior to screening **AND** with at least one of the following criteria at presentation:
 - A. Signs of some or severe dehydration as per WHO Pocket Book 2013

- B. Moderately wasted as defined by a mid-upper arm circumference (MUAC) less than 125 mm (but greater than or equal to 115 mm) or a weight-for-length z-score (WLZ) greater than -3SD and less than or equal to -2SD after rehydration during stabilization period or
- C. Severely stunted (length-for-age z-score (LAZ) <-3 SD) **AND**
- Parent or guardian (caregiver) willing to allow household visits on DAY 2 and DAY 3 and willing to return to facility on DAY 90 **AND**
- Parent or guardian (caregiver) provides a consent for trial participation on behalf of the child, based on local standards

Exclusion criteria (any one of):

- Dysentery (gross blood in stool reported by caregiver or observed by healthcare worker [HCW]),
- Suspected *Vibrio cholerae* infection (determined according to WHO guidelines or clinical suspicion),
- Previously or currently enrolled in the ABCD study,
- Concurrently enrolled in another interventional clinical trial,
- Sibling or other child in the household enrolled in the ABCD study and currently taking study medication,
- Signs of associated infections (pneumonia, severe febrile illness, meningitis, mastoiditis or acute ear infection) requiring antibiotic treatment,
- Documented antibiotic use in the 14 days prior to screening (not including standard use of prophylactic antibiotics, i.e. co-trimoxazole use in HIV-exposed children),
- Documented use of metronidazole within the last 14-days,
- Known allergy or contraindication to azithromycin antibiotics,
- Severe acute malnutrition (SAM) defined as WLZ less than -3 SD, or MUAC less than 115 mm, or edema of both feet, OR
- Living too far from the enrolment health center to ensure adequate Directly Observed Therapy (DOT) on DAY 2 and DAY3

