2.4 Intervention

3-day course of azithromycin or placebo

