5.2 Randomization and blinding

Randomization (1:1) will be done in random sized blocks (with varying block sizes of 4, 6 and 8). All drug and placebo will be procured by WHO MCA Department where a separate randomization list for each of the sites will be generated. This list will then be converted into a unique sequential serial number for each enrolled child for each site. The list provided to the site will only have these serial numbers with the first letter depicting the site. Individual child's supply of study drugs will be provided to each site and labeled with this serial number. At the sites, enrolled children will receive the drugs contained in the bottle with the randomization number identical to the enrolment number. The sites will not have the randomization code.

To ensure blinding, the number of bottles and doses for each of the two groups will be identical. The drug and control bottles and medications will be similar in all aspects including the content, color and taste. Treatment allocation (once assigned) will remain blinded to the participant, the site PI, the study site staff and the hospital clinicians during all data collection phases of the study.

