6.5 Collection and processing of biological specimens

A fecal sample will be collected from all children at enrolment. This sample will be aliquoted and stored at -80°C without further processing, to facilitate later molecular identification and analysis of enteric pathogens and their antimicrobial resistance genes.

A subset of up to 1600 to 1800 ABCD participants (approx. 15%) will be enrolled in a more detailed AMR sub-study. Random assignment into the AMR sub-study will be determined by the WHO Central Coordinating Office as part of the intervention randomization code, stratified by site and intervention arm. Children enrolled in the AMR sub-study will have a stool sample collected and processed at baseline, and a stool sample and a naso-pharyngeal swab collected

and processed for culture and resistance testing at DAY 90 and at DAY 180 after enrolment. In addition, a stool sample and a naso-pharyngeal swab will also be collected from a sibling or other close household contact (child contact) of the enrolled child (index-child) at DAY 90 and DAY 180.

The stool samples are primarily collected from whole stool passed by the study participant into a diaper or a container. If, however, the sample is taken at the study clinic (always on enrolment visit, sometimes on subsequent visits), and the child has not passed stool within 2-4 hours of the start of the clinic visit, and the primary caregiver gives a permission to the procedure, the stool sample may be taken with 2 cotton swabs, quickly inserted into the participant's rectum by a research nurse or physician.

Although it is determined at study enrolment whether the index child will participate in the AMR sub-study, no samples will be collected from the siblings or close household contacts before the 90 and 180-day time points. Eligible contacts are the participant's mother or children aged less than 60 months, who have slept in the same household as the enrolled child for 5 of the last 7-nights, and who share the same primary caregiver as the index child. If there are multiple contacts in the household who meet the eligibility criteria, then the preference for inclusion in the "contact study" will be given to the child closest in age and living in the same quarter as the index child. The contact will be the same child at DAY 90 and 180 so as to maintain the ability to evaluate within-individual change in resistance.

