9.6.2 Analysis

Four non-inferiority hypothesis tests (2 samples and 2 timepoints) will be conducted to test whether the difference in prevalence of resistance in children assigned to the azithromycin and placebo group exceeds 10% (one sided test).

E.coli Day 90

H₀: $R_{AZM} - R_{placebo} > 10\%$
H₁: $R_{AZM} - R_{placebo} \leq 10\%$

E.coli Day 180

H₀: $R_{AZM} - R_{placebo} > 10\%$
H₁: $R_{AZM} - R_{placebo} \leq 10\%$

S. pneumoniae Day 90

H₀: $R_{AZM} - R_{placebo} > 10\%$
H₁: $R_{AZM} - R_{placebo} \leq 10\%$

S. pneumoniae Day 180

H₀: $R_{AZM} - R_{placebo} > 10\%$
H₁: $R_{AZM} - R_{placebo} \leq 10\%$

Although this analysis is predefined, we anticipate low power for this analysis. Justification for the NI margin of 10%: this margin has been chosen based on clinical acceptability among

infectious disease experts. Also, consultation with investigators in other trials of azithromycin accept a 10% (absolute difference) NI margin as reasonable. The non-inferiority hypothesis will be tested using the continuity corrected χ^2 test as suggested by Dunnett and Gent, Biometrics 1977. Since all participants will not provide a contact for sampling (stool or swab), an examination for systematic bias among the contacts who provided samples that were submitted for testing (eg by date range, site) will be undertaken. Any apparent bias will be described, and potentially adjusted for using a modeling framework.

In the primary analysis, the denominator of these prevalence estimates will be all child contacts enrolled in the AMR sub-study whose stool was submitted for antimicrobial sensitivity testing (irrespective of whether the bacteria was isolated). Treatment of sites affected by COVID-19 lockdowns will be as outlined in Section 9.5.2.

In secondary analysis, the prevalence denominator will be defined as those contacts in whom the respective bacteria was isolated and tested (i.e. azithromycin resistance in *E. coli* as a proportion of *E. coli* isolates, and likewise for *S. pneumoniae*). Sites that have not completed testing as outlined above, will be dealt with as outlined in Section 9.5.2.

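### The contact resistance tests can include children randomized in their own right, which may slightly favour a non-inferiority conclusion (minor)

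*Protocol*

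**What the plan says.** - **Enrolment (Protocol 2.3).** Two exclusions matter. One covers the child itself: "Previously or currently enrolled in the ABCD study". The other covers the household: "Sibling or other child in the household enrolled in the ABCD study and currently taking study medication". The intervention is a "3-day course of azithromycin or placebo" (Protocol 2.4), so the household bar is short. Allocation is individual and 1:1 (Protocol 5.2).
- **Contacts (Protocol 6.5).** Eligible contacts are the mother or "children aged less than 60 months, who have slept in the same household as the enrolled child for 5 of the last 7-nights", with the same primary caregiver. If several qualify, preference "will be given to the child closest in age and living in the same quarter as the index child". On timing, "no samples will be collected from the siblings or close household contacts before the 90 and 180-day time points". Being outside the trial is not a condition.
- **Analysis (SAP 9.6 to 9.6.4).** Contacts are compared by the index child's arm. The hypotheses are one-sided with a 10-point margin, tested with a continuity-corrected chi-square. The primary denominator "will be all child contacts enrolled in the AMR sub-study whose stool was submitted for antimicrobial sensitivity testing". Nobody is removed for having received study drug.
- **Caveats already in the SAP.** Section 9.6 says that contact recruitment was not random and that bias is likely. Section 9.6.2 plans a check for systematic bias, with date range and site as examples, and expects low power. Section 9.6.4 adds exploratory adjustment that includes recent antibiotic use. None of these mentions contacts who were trial participants.

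**The concern.** Once the first child's course is over, another household child aged 2 to 23 months who meets the criteria can be enrolled and randomized, possibly to the other arm. The same can happen in reverse order, with the contact enrolled before the index child. Contacts are first sampled at day 90, so there is time for this. The closest-in-age preference, and a SAP denominator limited to child contacts, both lean towards children who could be of trial age.

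The contact test is there to show whether treating the index child raises resistance in the household. A contact dosed with azithromycin directly may already carry resistant organisms whatever the index child received, and such contacts would pull the two index arms together. The null hypothesis is an excess above 10 points, so a smaller observed difference makes it easier to conclude that the spread of resistance is acceptable. The same gap reaches the index comparison in SAP 9.5.2, because a placebo index child may live with an azithromycin-treated sibling.

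**Working it through.** **1. The plan's own figure.** Protocol 10.3 asks for 119 isolates per arm per region (20% versus 40%, 90% power, alpha 0.05).

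- Uncorrected: n = [1.960√(2 × 0.3 × 0.7) + 1.282√(0.2 × 0.8 + 0.4 × 0.6)]² / 0.2² = 108.2, so 109.
- Continuity-corrected: (n/4)[1 + √(1 + 4/(0.2n))]² = 118.0, so 119. The stated figure is reproduced.
- Loss chain in Table 2: 345 × 0.9 × 0.8 × 0.8 = 198.7, shown as 199 children with a contact. Then × 0.67 × 0.9 = 119.8, shown as 119.

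**2. Contacts per arm.** Protocol 10.3 expects about 1,000 children in Africa and 750 in Asia, so about 875 per arm. The primary contact denominator in SAP 9.6.2 does not need an isolate, so only the first three losses apply: 875 × 0.9 × 0.8 × 0.8 = 504.

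**3. Model.** Let f be the share of contacts who are themselves participants. It is not in the documents, so a range is assumed. With 1:1 allocation, f/2 received azithromycin directly. Let the true spillover be 10 points, exactly at the margin (20% versus 30%).

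- *Masking:* contacts who took azithromycin themselves have 30% resistance in both index arms (assumed). Then p0 = 0.20(1 − f/2) + 0.30(f/2), p1 = 0.30, and d = 0.10(1 − f/2).
- *Additive:* own treatment adds the same amount in both index arms, so d stays at 0.10 for any f.

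**4. Error rate.** Normal approximation, n = 504, one-sided 5%, continuity term 1/n = 0.00198:

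P(false non-inferiority) = Φ[(0.10 − d − 1/n)/SE − 1.645], with SE = √{[p0(1 − p0) + p1(1 − p1)]/n}.

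| f | p0 | d | SE | z | P |
|---|---|---|---|---|---|
| 0 | 0.2000 | 0.1000 | 0.0271 | −1.718 | 4.3% |
| 2% | 0.2010 | 0.0990 | 0.0271 | −1.681 | 4.6% |
| 5% | 0.2025 | 0.0975 | 0.0271 | −1.626 | 5.2% |
| 10% | 0.2050 | 0.0950 | 0.0272 | −1.534 | 6.3% |

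Under masking, the shrinkage cancels the continuity term when 0.10 × f/2 = 1/504, that is f = 4.0%. Below that the error stays under 5%. In the additive case it stays at about 4.3%.

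**5. Sensitivity.**

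- The SAP states no alpha for these one-sided tests. At 2.5% the four values are 2.1%, 2.3%, 2.6% and 3.2%.
- With 199 contacts per arm at 5%, they are 3.9%, 4.1%, 4.4% and 5.0%.
- Under masking, bringing a true difference s down to 10 points needs f = 2(1 − 10/s): 18% for 11 points, 33% for 12 and 67% for 15.

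**The case against.** **Stronger readings that a reader might infer.** One is that the test is always diluted in the unsafe direction. The documents do not support that: f is unknown and could be zero, and additive effects give no dilution.

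Another is that every co-enrolled contact shows no index-arm difference, so that d = 0.10(1 − f). Without a continuity correction that gives 5.0%, 5.8%, 7.2% and 10.1% at the same four values of f. It overstates the problem, because the half on placebo can still show spillover and SAP 9.6.2 specifies the correction. Nor does either document call the contacts untreated.

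**Limits on f and on its effect.** An affected contact must share the caregiver, have qualified while aged 2 to 23 months, have been enrolled separately and have been dosed before sampling. Protocol 11 says that macrolide resistance falls quickly once treatment stops. Recruitment was halted early (SAP 2), and lockdowns may remove samples or whole sites, so there may be fewer than 504 contacts per arm, which reduces the inflation. All of this stands, and it is why the point is minor.

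**Estimand.** Comparing contacts by index arm is a coherent household-level contrast, and a contact's independent allocation does not confound it. Excluding co-enrolled contacts conditions on something that may follow the index child's randomization. That is fair but of limited force, since contacts are already chosen non-randomly at day 90. It is a reason to keep the all-contact result in view.

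**Existing caveats.** They lower the weight placed on the contact result, but they neither identify nor remove directly dosed children.

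**Conclusion.** The gap is real: nothing in Protocol 2.3, Protocol 6.5 or SAP 9.6 keeps children with their own allocation out of the contact tests. The statistical consequence is conditional and small. It needs co-enrolled contacts to exist and own azithromycin to mask spillover. The attenuation is then about f/2 and favours non-inferiority. On the assumptions above, the error at the margin is still only 5.2% at f = 5% and 6.3% at f = 10%. These figures rest on an assumed f, 20% resistance in the placebo index arm, full sub-study recruitment and a one-sided 5% level.

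Apart from the error rate, the result is harder to read as household spread if an unreported number of contacts took the drug themselves. That number can be found and should be reported. Severity: minor.

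**What to change.** Amend the SAP before the intervention code is broken; SAP 6.4 foresees amendments at that stage.

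1. Link contacts to the enrolment register. Report, by index arm, how many had an ABCD number dated before the sample.
2. Run the SAP 9.6.2 tests on contacts without prior ABCD enrolment of their own. Show the all-contact analysis alongside, because co-enrolment can follow the index child's randomization.
3. Add to SAP 9.5.2 a sensitivity analysis without index children who had another ABCD participant in the household before the sample.

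Rewording contact eligibility in Protocol 6.5 would not help now. The last participants were recruited on 10 July 2019 (SAP 2), so day 180 fell in early January 2020, before the SAP was finalized in May 2020. No enrolment or treatment rule needs to change.

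The cost is the linkage and the loss of a few contacts from an analysis already expected to have low power. The documents describe no household identifier, so the linkage effort cannot be judged from them.
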